1.1.1. Estimands

1.1.1.1. Primary and Supportive Estimands for Induction Period

There will be three estimands of interest in analyzing primary and key secondary endpoints for the Induction Period. Two types of intercurrent events in terms of estimating the treatment effects for the Induction Period will be considered: initiation of rescue medication as defined in Section 6.6.1 and permanent treatment discontinuation.

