4.1.6.1.1. Markov Chain Monte Carlo Multiple Imputation (MCMC-MI)

The primary method of handling missing efficacy data relative to the primary estimand will be as follows for both binary and continuous endpoints:

For participants who receive rescue medication (i.e., high-potency TCS or systemic AD treatment, defined in [Appendix 13](#)), or discontinue treatment due to lack of efficacy, set to the participant's baseline value subsequent to this time through Week 16. The MCMC-MI will be used to handle the remaining missing data. Imputation will be conducted within each treatment group independently so the pattern of missing observations in one treatment group cannot influence missing value imputation in another. The SAS PROC MI with MCMC option will be used to conduct the MCMC-MI. The imputation model will include the relevant baseline and post-baseline.

For each imputation process, 25 datasets with imputations will be calculated. The initial seed values are given in the table below. Each complete data set will be analyzed with the specified analysis. The results from these analyses will be combined into a single inference using SAS PROC MIANALYZE.

CMH test statistic will be transformed using the Wilson-Hilferty transformation and then standardized (Ratitch 2013) prior to combining them using SAS PROC MIANALYZE. Details of combining estimates and test statistics for categorial endpoints with multiple imputation can be found in [Appendix 14](#).

For binary responses related to EASI and IGA, the binary response variables will be calculated based on the multiply imputed datasets that have been created. Because the MCMC algorithm is based on the multivariate normal model, imputed values for IGA will not generally be one of the discrete values used in IGA scoring (0, 1, 2, 3, or 4). Therefore, to derive the binary IGA response variable, standard rounding rules will be applied to the imputed values. For example, if a participant has an IGA score imputed as 1.4 (and assuming a Baseline IGA score of 3), the imputed value would be rounded down to 1, and the minimum change from Baseline of 2 would have been met. This participant would be considered a responder.

For derivation of an EASI-75 and EASI-90 response, no rounding will be performed. The imputed Week 16 EASI value will be compared directly to the observed Baseline EASI value to determine whether a reduction of at least 75% or 90% was achieved.

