4.1.6.1.3. Non-responder Imputation

The non-responder imputation (NRI) method will be used to handle missing data relative to the supportive estimand for categorical endpoints (composite). Participants who receive rescue medication (i.e., high-potency TCS or systemic AD treatment, defined in [Appendix 13](#)), or discontinue treatment, will be set to non-response subsequent to this time through Week 16. Intermittent missing values will also be set to non-response.

The non-responder imputation (NRI) method imputes missing values as non-responders and can be justified based on the composite strategy (ICH E9 R1) for handling intercurrent events. In this strategy, participants are defined as responders only if they meet the clinical requirements for

response at the predefined time AND they remain on the assigned study treatment (i.e., not using rescue medications and not having missing values due to other reasons). Failing either criteria by definition makes them non-responders.

Randomized participants without at least 1 post-baseline observation will also be defined as non-responders for all visits for the NRI analysis.

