4.1.6.1.4. Mixed-effects Model for Repeated Measures (MMRM)

Mixed-effects model for repeated measures analyses will be performed on continuous endpoints to mitigate the impact of missing data. This approach assumes missing observations are missing-at-random (missingness is related to observed data) and borrows information from participants in the same treatment arm taking into account both the missingness of data through the correlation of the repeated measurements.

The values subsequent to rescue medication use (i.e., high-potency TCS or systemic AD treatment, defined in [Appendix 13](#)) or treatment discontinuation will be made missing before applying the MMRM model. The MMRM model is described in Section [4.1.1](#).

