4.1.6.1.5. Last Observation Carried Forward (LOCF)

In this analysis, the values subsequent to rescue medication use (i.e., high-potency TCS or systemic AD treatment, defined in [Appendix 13](#)) or treatment discontinuation will be made missing. All missing values will be imputed using LOCF. Baseline value will be used for imputation if there is no post-baseline observation.

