4.3.2. Main analytical approach

The primary analysis of the study is to test the co-primary null hypotheses described in Section 2 in the ITT Population.

The primary estimand addresses the treatment response as directed. The analysis assumes that treatment response disappears for participants who took rescue medication (i.e., high-potency TCS or systemic AD treatment, defined in [Appendix 13](#)) or withdrew from the study due to lack of efficacy, therefore setting to the participant's baseline value subsequent to this time through

Week 16. Other missing values will be imputed using MCMC-MI based on missing at random assumption (Section 4.1.6.1.1).

A CMH test as described in Section 4.1.1 will be used for the comparisons. The OR, the corresponding 95% CIs and p-value, as well as the treatment differences and the corresponding 95% CIs, will be reported.

Multiplicity controlled analyses will be performed on the primary and key secondary endpoints to control the overall Type I error rate at a 2-sided alpha level of 0.05. A graphical approach will be used to perform the multiplicity controlled analyses as described in Section 2.1.

The analyses for primary outcomes of EASI-75 and IGA score of 0 or 1 are described in [Appendix 2](#).

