6.6.1. Rescue Medication for Atopic Dermatitis (AD)

Rescue medication for AD is defined as:

- any high-potency TCS as defined in [Appendix 13](#), and the response to the question “For what indication was the medication / therapy taken?” on the Concomitant Therapy eCRF page is “Rescue Therapy”
- any systemic medication as defined in [Appendix 13](#), and the response to the question “For what indication was the medication / therapy taken?” on the Concomitant Therapy eCRF page is “Rescue Therapy”

Participants who use these rescue medications will be summarized. The summary will be provided for any rescue medication use, with high-potency TCS and systemic therapy summarized separately for the Induction Period on the ITT Population, the Maintenance Blinded Period on the MPP, and the Maintenance Escape Period on the Maintenance W16 Escape Population, respectively.

Disease flares will be assessed based on rescue therapy usage. Flare is defined as initiation or intensification of rescue therapy. A summary of percentage of participants in the ITT Population, the MPP, and the Maintenance W16 Escape Population rescued by visit will be provided for the

Induction Period, Maintenance Blinded Period, and Maintenance Escape period, respectively. Kaplan-Meier curves for time to first rescue use may be generated.

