POEM is collected every week via eCOA, the visit week mapping will follow the following rule: the last collected POEM data before or on the visit date would be used, the evaluation window is injection date – 7 to injection date – 1 for baseline and assessment date – 7 to assessment date – 1 for post-baseline. For example, if a participant gets an injection/assessment on the 14th, the scale completed between the 13th and the 7th would be used.

6.13. **Appendix 13: Definition of Topical and Systemic Atopic Dermatitis Therapy**

The atopic dermatitis therapy in this study is defined as: high-potency TCS and systemic atopic dermatitis therapy. The topical treatments and systemic treatments are defined as following:

1. **Topical Atopic Dermatitis Treatment (including corticosteroids, TCI and crisaborole)**

Route of topical treatments includes: Topical and Transdermal.

Corticosteroids (TCS):

High-potency TCS: ATC code is D07, and the response to the item “If topical, collect Potency” on the Concomitant Therapy eCRF page is “High”.

Low or Moderate-potency TCS: ATC code is D07, and the response to the item “If topical, collect Potency” on the Concomitant Therapy eCRF page is “Low” or “Moderate”.

Topical calcineurin inhibitor (TCI): Preferred Term includes: TACROLIMUS, PIMECROLIMUS

Crisaborole: Preferred Term includes: CRISABOROLE

Topical JAK (Janus kinase) inhibitor: Preferred Term includes: DELGOCITINIB

Topical PDE4 (phosphodiesterase 4) inhibitor: Preferred Term includes: DIFAMILAST

2. Systemic Atopic Dermatitis Treatment (including oral corticosteroids, immunosuppressant, biologics and phototherapy/photochemotherapy)

Route of systemic treatments administration includes: Oral, Intra-Arterial, Intramuscular, Intraperitoneal, Intravenous, Subcutaneous, Transdermal. (This condition applies to the following categories except for phototherapies.)

Systemic Corticosteroids: ATC code is H02

Immunosuppressant: Defined as: ATC2 is L04 or Preferred terms of Abrocitinib, Baricitinib, Upadacitinib or Ruxolitinib

Biologics: Defined as following Preferred terms:

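### The SAP words the Induction rescue rule in two ways, and the version its estimand cites can miss a corticosteroid course that the protocol treats as rescue

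*SAP*

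**What the plan says.** **Estimand.** SAP 1.1.1.1 names two Induction intercurrent events: "initiation of rescue medication as defined in Section 6.6.1 and permanent treatment discontinuation". SAP 6.6.1 sets two conditions for rescue: a high-potency TCS or systemic medication as defined in Appendix 13, and an answer of Rescue Therapy to the Concomitant Therapy eCRF item "For what indication was the medication / therapy taken".

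**Analysis sections.** SAP 4.1.6.1.1, the primary imputation, reads "For participants who receive rescue medication (i.e., high-potency TCS or systemic AD treatment, defined in" Appendix 13, and sets such values to baseline through Week 16. SAP 4.3.2, the co-primary analysis, refers to "participants who took rescue medication (i.e., high-potency TCS or systemic AD treatment, defined in" Appendix 13. NRI (4.1.6.1.3), MMRM (4.1.6.1.4) and LOCF (4.1.6.1.5) use the same formula, for example "The values subsequent to rescue medication use (i.e., high-potency TCS or systemic AD treatment, defined in" Appendix 13. The tipping-point section (4.1.6.1.2) points to neither definition.

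**Appendix 13.** It classifies by ATC code or preferred term, by route and, for TCS, by recorded potency. A typical entry is "Systemic Corticosteroids: ATC code is H02", with a systemic route. It has no indication condition.

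**Protocol.** Section 6.5.1 says that a systemic corticosteroid used for an AE, such as an asthma exacerbation, is still treated as rescue. Section 6.5.3 requires all rescue use to be recorded in the eCRF. Section 6.5 requires concomitant medication to relate to an AE or medical history, apart from supplements and preventive care. Section 9.4.1.1, the protocol's imputation rule, describes rescue as high- or ultra-high-potency TCS or systemic AD treatment.

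**The concern.** The rescue rule decides whose EASI and IGA are set to baseline, and so who counts as a non-responder, in both co-primary analyses. Two programmers working from this SAP could derive different Week 16 flags for anyone who took a listed drug that was not coded as rescue therapy.

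There is also a conflict with the protocol that does not depend on which SAP wording is meant to govern. If 6.6.1 governs and a site records the AE as the indication, a corticosteroid course that protocol 6.5.1 treats as rescue is not counted. SAP 4.9 lists no such departure.

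A smaller, descriptive matter sits beside this. Protocol 9.3 limits the Maintenance Primary Population (MPP) to participants re-randomized at Week 16 or continuing Q4W, and protocol 6.3 excludes rescued participants from the responders. The MPP definition in SAP 3 states neither condition.

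**Working it through.** **1. The rules side by side**

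| Drug taken in Induction | SAP 6.6.1 | Analysis sections, read literally | Protocol |
|---|---|---|---|
| Listed high-potency TCS or systemic drug, coded Rescue Therapy | Rescue | Rescue | Rescue (6.5.3) |
| Systemic corticosteroid for an AE, coded otherwise | Not rescue | Rescue by drug code and route | Rescue under 6.5.1; unclear under 9.4.1.1 |
| Other listed high-potency TCS or systemic drug, coded otherwise | Not rescue | Rescue by drug code | No indication field mentioned |

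**2. What happens to the second row under 6.6.1**

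- *Imputed path.* If study drug is stopped for a reason other than lack of efficacy, the Week 16 value is set to missing and imputed by MCMC-MI. NRI covers this path, because any treatment discontinuation is non-response. So does the tipping-point analysis, which is run only after a significant result and takes missing lebrikizumab responses down to probability 0.
- *Observed path.* If study drug continues, the value is used as observed. It is neither missing nor after a recognized intercurrent event, so NRI and tipping point leave it unchanged. The per-protocol repeat may remove some of these participants: SAP 6.7 gives interfering concomitant medication as a possible important deviation. The actual exclusions are in the Trial Issues Management Plan.

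**3. The plan's own power figures**

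The inputs are 120, 80 and 80 participants, the assumed rates in SAP 5, and a two-sided Fisher exact test at 0.05. Exact enumeration gives:

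- Q2W: IGA 98.0%, EASI-75 99.98%; joint power at least 0.9795 + 0.9998 − 1 = 97.9%.
- Q4W: IGA 82.5%, EASI-75 99.1%; joint power at least 0.8254 + 0.9906 − 1 = 81.6%.

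The stated >95% and >80% reproduce and are not in dispute.

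**4. Shift per reclassified participant, compared with setting to baseline**

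- Observed path: 0 to 100/80 = 1.25 points in an 80-participant arm; 0 to 100/120 = 0.83 in the Q2W arm.
- Imputed path, assuming the imputed response probability equals the planned rate, in the order Q4W, Q2W, placebo:
  - IGA: 33/80 = 0.41, 38/120 = 0.32, 13/80 = 0.16.
  - EASI-75: 53/80 = 0.66, 58/120 = 0.48, 20/80 = 0.25.

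**5. How many reclassifications would change significance**

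Planned counts are rate × n, rounded: IGA 0.38 × 120 = 46, 0.33 × 80 = 26, 0.13 × 80 = 10; EASI-75 Q4W 0.53 × 80 = 42, placebo 0.20 × 80 = 16. Each margin assumes no offset in the other arm.

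| Comparison | Start | Placebo responders added | Active responders removed |
|---|---|---|---|
| IGA, Q4W | 26/80 v 10/80, p=0.0041 | 5 (p=0.069; 4 gives 0.044) | 6 (p=0.067; 5 gives 0.044) |
| IGA, Q2W | 46/120 v 10/80, p=0.0001 | 10 (p=0.065; 9 gives 0.032) | 18 (p=0.066; 17 gives 0.046) |
| EASI-75, Q4W | 42/80 v 16/80, p<0.001 | 13 (p=0.056; 12 gives 0.038) | 14 (p=0.051; 13 gives 0.034) |

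This is Fisher on complete counts, as in the sample-size section, not the planned CMH test on imputed data. It takes 0.05 as the level for every comparison; the testing graph is a figure that is not shown.

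**6. MPP overlap**

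A lebrikizumab participant who is rescued in Induction, meets IGA 0/1 or EASI-75 at Week 16 and is dosed in the Escape Arm meets both the MPP and the W16 Escape definitions. All three MPP treatment groups are responder groups that stay on blinded treatment, so probably only the Total column could include this person. At planned EASI-75 rates the MPP has about 0.58 × 120 + 0.53 × 80 = 112 members, so one more shifts Total by at most about 100/113 = 0.88 points.

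**The case against.** The best defense is that 6.6.1 governs throughout. SAP 4.1.6, the parent of the imputation sections, refers to 1.1.1 for the estimands, and 1.1.1.1 refers to 6.6.1. Appendix 13 behaves like a dictionary: it also classifies past and concomitant AD treatment, includes permitted background topicals, and is itself called by 6.6.1. This reading is plausible, and a reader should not infer that the SAP never connects the two definitions. What remains is that 4.3.2 names the primary estimand but cites neither 1.1.1 nor 6.6.1, and that each analysis section introduces Appendix 13 with i.e., which states an equivalence.

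Second, sites may well code these courses as rescue, since protocol 6.5.1 calls them rescue and 6.5.3 requires rescue use to be recorded. That is fair. The eCRF completion instructions are not in the documents, so it cannot be said that such courses will be missed, only that the SAP rule depends on how they are coded.

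Third, the observed path is narrow. Protocol 6.5.1 sends the case to 6.5.3, which requires study intervention to stop when systemic treatment is needed by Week 16. Exclusion criterion 10 also makes oral corticosteroid bursts less likely. Both points stand and limit the size.

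Fourth, the protocol is not of one mind: the AD wording of 9.4.1.1 is in tension with 6.5.1. This also stands. It means the reconciliation must take in the protocol as well, and that 6.5.1 cannot be stretched to every systemic corticosteroid whatever its indication. It speaks only of courses for AD or for an AE.

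On the MPP, the SAP presents only pre-escape information, and 4.9 records that the maintenance populations were updated. The overlap in the definition remains, but with little effect.

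**Conclusion.** The inconsistency is real and should be fixed. The estimand cites a rule with an indication condition, the analysis sections are worded without one, and the cited rule can depart from protocol 6.5.1 on a point that determines responder status in both co-primary analyses.

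A reader might infer that the co-primary conclusions are in doubt. The documents do not support that. The number of participants classified differently is not given and is probably small. The direction is unknown, because reclassification can occur in any arm. Even the weakest comparison needs 5 or 6 one-sided reclassifications at planned rates, and Q2W IGA needs 10 or 18. NRI and tipping point cover the imputed path; the observed path is narrow and may be partly covered by the per-protocol repeat. These margins assume the planned rates, complete counts and a 0.05 level.

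The MPP overlap is a defect of definition only. SAP 4.1.2.1 provides no inferential statistics for that population.

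**What to change.** Before unblinding:

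1. Write one rescue definition and cite it in SAP 1.1.1, 4.1.6 (including the tipping-point section), 4.3.2 and 6.6.1. Describe Appendix 13 as the drug list only.
2. Reconcile that definition with protocol 6.5.1 and 9.4.1.1. For the systemic corticosteroid courses that 6.5.1 already classes as rescue (for AD or for an AE), the derivation should not rely on the indication field alone. For the other listed classes, state whether the indication condition applies.
3. Record any departure from the protocol in SAP 4.9.
4. In SAP 3, restore to the MPP definition the protocol's condition that participants were re-randomized or continued Q4W. In Appendix 2, correct the maintenance rows for IGA and EASI response that speak of re-randomized participants, because Q4W responders are not re-randomized.

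The cost is SAP wording and two derivations. Nothing changes for sites or participants.

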6.7. Appendix 7: Protocol Deviations

Protocol deviations will be identified throughout the study. Important protocol deviations are defined as those deviations from the protocol likely to have a significant impact on the completeness, accuracy, and/or reliability of the study data or that may significantly affect a participant's rights, safety, or well-being. Out of all important protocol deviations (IPDs) identified, a subset occurring during the Induction Period with the potential to affect primary efficacy analysis will result in exclusion from the PPS.

Potential examples of important protocol deviations include participants who violated the inclusion/exclusion criteria, used an interfering concomitant medication, significant non-compliance with study intervention (<75% of expected injections). Refer to a separate document called "KGAL Trial Issues Management Plan" for the important protocol deviations with categorizations and whether or not these deviations will result in the exclusion of participants from the PPS.

The number and percentage of participants having IPD(s) will be summarized within category and subcategory of deviation by treatment group for the Induction Period on the ITT Population and for the Maintenance Period on All Maintenance Population.

A by-participant listing of important protocol deviations will be provided for the ITT population.

6.8. Appendix 8: Impact of COVID-19

Impact of pandemic (e.g., COVID-19) on analyses will be systematically addressed prior to study unblinding at Week 16 DBL, once the impact on study conducts is fully understood. In general, any missing assessments/visit window will be documented as protocol deviations. For participants who have missing assessments at Week 16 due to COVID-19, these patients may enter the escape arm. A summary or listing may be provided to summarize missing visits due to COVID-19.

Treatment discontinuation due to pandemic will be treated the same type of intercurrent event as treatment discontinuation due to reasons other than lack of efficacy. Strategies of how this type of intercurrent event will be handled are described in Section 1.1.1. Intermittent missing assessment due to pandemic will be treated the same as any other intermittent missing values. Details of how missing data will be handled are described in Section 4.1.6.

6.9. Appendix 9: Annual Report Analyses

Based on regulatory requirements for the Development Safety Update Report (DSUR), reports will be produced (if not already available from the study CSR) for the reporting period covered by the DSUR.

6.10. Appendix 10: Clinical Trial Registry Analyses

Additional analyses will be performed (if not already available from the study CSR) for the purpose of fulfilling the Clinical Trial Registry (CTR) requirements.

Analyses provided for the CTR requirements include the following:

Summary of AEs, provided as a dataset, will be converted to an XML file. Both serious adverse events (SAEs) and 'Other' AEs are summarized by treatment group and by MedDRA PT.

- An AE is considered 'Serious' whether or not it is a TEAE.
- An AE is considered in the 'Other' category if it is both a TEAE and is not serious. For each SAE and 'Other' AE, for each term and treatment group, the following are provided:
 - the number of participants at risk of an event,
 - the number of participants who experienced each event term, and
 - the number of events experienced.
- Consistent with www.ClinicalTrials.gov requirements, 'Other' AEs that occur in fewer than 5% of participants in every treatment group may not be included if a 5% threshold is chosen (5% is the minimum threshold).
- AE reporting is consistent with other document disclosures for example, the CSR, manuscripts, and so forth.

6.11. Appendix 11: Unblinding Plan

Unblinding details are specified in the BUP.

6.12. Appendix 12: Study Visit Mapping for Itch NRS, Skin Pain NRS and Sleep-loss and POEM

Itch NRS, Skin Pain NRS and sleep loss are collected via eCOA; entries will be mapped to study week by the following:

Week	Start Day	End Day
Baseline	Date of First Injection ^a - 7	Date of First Injection - 1
Week 1	Max (Date of First Injection, Week 2 Assessment Date - 14)	Week 2 Assessment Date - 8
Week 2	Week 2 Assessment Date - 7	Week 2 Assessment Date - 1
Week 4	Week 4 Assessment Date - 7	Week 4 Assessment Date - 1
Week 6	Week 6 Assessment Date - 7	Week 6 Assessment Date - 1
Week 8	Week 8 Assessment Date - 7	Week 8 Assessment Date - 1
Week 10	Week 10 Assessment Date - 7	Week 10 Assessment Date - 1
Week 12	Week 12 Assessment Date - 7	Week 12 Assessment Date - 1
Week 14	Week 14 Assessment Date - 7	Week 14 Assessment Date - 1
Week 16	Week 16 Assessment Date - 7	Week 16 Assessment Date - 1
Week 20	Week 20 Assessment Date - 7	Week 20 Assessment Date - 1
Week 24	Week 24 Assessment Date - 7	Week 24 Assessment Date - 1
Week 28	Week 28 Assessment Date - 7	Week 28 Assessment Date - 1

Week 32	Week 32 Assessment Date – 7	Week 32 Assessment Date – 1
Week 36	Week 36 Assessment Date – 7	Week 36 Assessment Date – 1
Week 40	Week 40 Assessment Date – 7	Week 40 Assessment Date – 1
Week 44	Week 44 Assessment Date – 7	Week 44 Assessment Date – 1
Week 48	Week 48 Assessment Date – 7	Week 48 Assessment Date – 1
Week 52	Week 52 Assessment Date – 7	Week 52 Assessment Date – 1
Week 56	Week 56 Assessment Date – 7	Week 56 Assessment Date – 1
Week 60	Week 60 Assessment Date – 7	Week 60 Assessment Date – 1
Week 64	Week 64 Assessment Date – 7	Week 64 Assessment Date – 1
Week 68	Week 68 Assessment Date – 7	Week 68 Assessment Date – 1

a If date of first injection is missing, the randomization date will be used.

If multiple assessments on a single day are present, use the first assessment. If an assessment could be mapped to different weeks, it will be mapped to the earlier week. Derivation of the weekly mean scores for Itch NRS, Skin Pain NRS and Sleep-loss could be found in [Appendix 1](#). If at least 1 of the 7 days contains non-missing daily assessments, post-baseline weekly score will be calculated using prorated weekly average. If the range of 7 days are all missing daily assessments, then the weekly score is missing.

POEM is collected every week via eCOA, the visit week mapping will follow the following rule: the last collected POEM data before or on the visit date would be used, the evaluation window is injection date – 7 to injection date – 1 for baseline and assessment date – 7 to assessment date – 1 for post-baseline. For example, if a participant gets an injection/assessment on the 14th, the scale completed between the 13th and the 7th would be used.

6.13. **Appendix 13: Definition of Topical and Systemic Atopic Dermatitis Therapy**

The atopic dermatitis therapy in this study is defined as: high-potency TCS and systemic atopic dermatitis therapy. The topical treatments and systemic treatments are defined as following:

1. **Topical Atopic Dermatitis Treatment (including corticosteroids, TCI and crisaborole)**

Route of topical treatments includes: Topical and Transdermal.

Corticosteroids (TCS):

High-potency TCS: ATC code is D07, and the response to the item “If topical, collect Potency” on the Concomitant Therapy eCRF page is “High”.

Low or Moderate-potency TCS: ATC code is D07, and the response to the item “If topical, collect Potency” on the Concomitant Therapy eCRF page is “Low” or “Moderate”.

Topical calcineurin inhibitor (TCI): Preferred Term includes: TACROLIMUS, PIMECROLIMUS

Crisaborole: Preferred Term includes: CRISABOROLE

Topical JAK (Janus kinase) inhibitor: Preferred Term includes: DELGOCITINIB

Topical PDE4 (phosphodiesterase 4) inhibitor: Preferred Term includes: DIFAMILAST

2. Systemic Atopic Dermatitis Treatment (including oral corticosteroids, immunosuppressant, biologics and phototherapy/photochemotherapy)

Route of systemic treatments administration includes: Oral, Intra-Arterial, Intramuscular, Intraperitoneal, Intravenous, Subcutaneous, Transdermal. (This condition applies to the following categories except for phototherapies.)

Systemic Corticosteroids: ATC code is H02

Immunosuppressant: Defined as: ATC2 is L04 or Preferred terms of Abrocitinib, Baricitinib, Upadacitinib or Ruxolitinib

Biologics: Defined as following Preferred terms:

Infliximab, Infliximabum, Etanercept, Etanerceptum, Adalimumab, Adalimumabum, Certolizumab, Certolizumabum, Certolizumab pegol, Golimumab, Golimumabum, Ozoralizumab, Afelimumab, Afelimumabum, Tumor Necrosis Factor Alpha (TNF-) Inhibitors, Tabalumab, Tregalizumab, Anakinra, Basiliximab, Basiliximabum, Daclizumab, Daclizumabum, Tocilizumab, Tocilizumabum, Mepolizumab, Mepolizumabum, Rilonacept, Rilonaceptum, Ustekinumab, Canakinumab, Briakinumab, Fezakinumab, Sirukumab, Sarilumab, Lebrikizumab, Secukinumab, Olokizumab, Gevokizumab, Brodalumab, Ladarixin, Ixekizumab, Dupilumab, Tildrakizumab, Tildrakizumabum, Reslizumab, Reslizumabum, Guselkumab, Guselkumabum, Olamkicept, Fletikumab, Bimekizumab, Mirikizumab, Risankizumab, Abatacept, Ligelizumab, Vedolizumab, Belimumab, Nemolizumab, Tralokinumab, Omalizumab

Phototherapy or Photochemotherapy:

Programming search of medication name (actual term or preferred term) contains ‘photo’ or ‘UV’ then medicals to manually review to confirm whether the medication in question is indeed ‘Phototherapy’ or ‘Photochemotherapy’

6.14. Appendix 14: Details of Combining Estimates and Test Statistics for Categorical Endpoints with Multiple Imputation

Following the implementation of MCMC-MI imputation as specified in Section 4.1.6.1.1, the 25 data sets with imputations should be set together and sorted by imputation number. The following sections describe the processes for combining inferences for the individual imputed data sets into one inference for reporting. All calculations are performed in SAS software version 9.4.

Summarize Unadjusted Response Rate

The response rates, overall and by treatment arm, and their associated SEs are computed for each imputed data set using PROC FREQ with the *riskdiff* option specified for the appropriate column in the TABLES statement. The response rates and SEs from the resulting output are combined across the 25 imputed data sets using PROC MIANALYZE, separately for each arm and the overall group.

Note that the estimate and 95% CI bounds output by PROC MIANALYZE are percents (i.e., they are in terms of the response rate). To obtain the number of responders, the estimated percent is multiplied by the number of individuals in the analysis population and rounded to the nearest integer.

Compute Stratified Measures of Association

The common risk difference, common OR, and CMH test statistic are computed for each imputed data set using PROC FREQ with the *riskdiff* option for the appropriate column (for risk difference) and the *cmh* option (for OR and CMH test statistic) specified in the TABLES statement. Each of these analyses are stratified by age group, and baseline disease severity via inclusion of these variables in the TABLES statement with the treatment and outcome variables.

Note that the PROC FREQ output corresponding to the Mantel-Haenszel method is used for the risk difference, and the output corresponding to the General Association statistic is used for the CMH statistic. PROC MIANALYZE is then called separately for each of these measures, with further details in the sections below.

Common Risk Difference

No transformation is necessary before using PROC MIANALYZE to combine the risk difference estimates and their associated SEs across the 25 imputed data sets. This procedure outputs an estimate of the common risk difference and the associated 95% CI bounds.

Common Odds Ratio

The OR from each imputed data set is first transformed using the natural logarithm. The SE for each log OR (SE_{log}) is derived from the OR 95% CI bounds (LB_{OR} , UB_{OR}) according to the following equation: $SE_{log} = (\ln(UB_{OR}) - \ln(LB_{OR}))/2 \times 1.96$. The log OR and derived SE are then combined using PROC MIANALYZE, which outputs a combined estimate of the log OR and the associated 95% CI. Finally, these measures can be exponentiated to transform them back to the OR scale.

Cochran-Mantel-Haenszel Test

The CMH test statistic (CMH) from each imputed data set is transformed using the Wilson-Hilferty transformation and standardized so that it has approximately a standard Normal distribution (Ratitch 2013). In particular, the transformed CMH statistic is computed as follows:

$$CMH_{WH} = \frac{\left(\frac{CMH}{df}\right)^{\frac{1}{3}} - \left(1 - \frac{2}{9 \times df}\right)}{\sqrt{\frac{2}{9 \times df}}}, \text{ where } df \text{ is the degrees of freedom of the CMH statistic. Then the}$$

SE for each CMH_{WH} is 1, and PROC MIANALYZE is used to output a combined estimate of the transformed CMH statistic. Note that the two-sided p-value output by PROC MIANALYZE is not used directly, but instead the one-sided p-value is computed manually using both the t statistic and two-sided p-value output by PROC MIANALYZE: if t statistic is greater than 0,

